4.7 OFF-STUDY CRITERIA

Criteria that can take a participant off-study include:

- Participant requests to be withdrawn from study without further follow-up,
- Completed study follow-up period,
- Death,
- Screen failure

4.8 STUDY DISCONTINUATION

This study may be temporarily suspended or prematurely terminated if there is sufficient reasonable cause. Written notification, documenting the reason for study suspension or termination, will be provided by the suspending or terminating party to Novocure, IRB, and other regulatory authorities as needed. If the study is prematurely terminated or suspended, the Investigator will promptly inform the IRB and will provide the reason(s) for the termination or suspension. Reasons for terminating the study may include the following:

- Incidence or severity of adverse events, in this or other studies, indicates a potential health hazard to participants.
- Demonstration of efficacy that would warrant stopping.
- Data that are not sufficiently complete and/or evaluable.
- Investigator(s) do not adhere to the study protocol, or applicable regulatory guidelines in conducting the study.
- Participant enrollment is unsatisfactory.
- Submission of knowingly false information from the study site to Novocure, or local or other regulatory authorities.
- Upon instruction by local or other regulatory, or oversight authority.

Study may resume once concerns about safety, protocol compliance, data quality are addressed and satisfy the Sponsor, IRB and/or FDA.

5. INVESTIGATIONAL PRODUCT

A list of the adverse events and potential risks associated with the investigational or other agents administered in this study can be found in Section 9.4.

5.1 OPTUNE®

The second generation Optune® device weighs 2.7 lbs and the treatment kit is comprised of the following components: an Electric Field Generator, INE Insulated Transducer Arrays (i.e., the transducer arrays), and additional device components that include a power supply, portable battery, battery rack, battery charger, connection cable and carrying case (**Figure 2**).

The investigator, or other qualified designee, will provide participants, as well caregiver or family member (if needed), with training and instruction on how to operate the Optune® device for continuous at-home treatment. Along with providing training and instruction, participants issued an Optune® device will be provided a patient information and operation manual.

Please refer to patient information and operation manual for instructions on using device.

ACQUISITION

The Optune® device and components of the treatment kit will be supplied by manufacturer (Novocure, Inc) to the individual participant. Transducer arrays will be shipped as per company's policy.

For investigator and study team: The manufacturer will contact each participant after eligibility is confirmed and the individual is enrolled on the study. A nurse coordinator, or other designated healthcare provider, from Novocure Inc. will meet with each participant to discuss the application of device, skin care, in the same way patients with GBM are started on the device.

For participants: Participants are required to make arrangements with Novocure Inc. representative for this study to arrange for replacement of device parts and transducer arrays.

DEVICE COMPONENTS

5.1.1.1 Optune Electric Field Generator

The Optune Electric Field Generator is a portable, battery or power supply operated device. The outputs are connected to two pairs of insulated transducer array sets operated sequentially. The intensity of the field, the frequency of the waves, and the temperature of the transducer arrays are pre-set, and are controlled by two microcontrollers that run Novocure's software. The output parameters of the Electric Field Generator are either pre-programmed or set by the service technician through a "service only" USB-type connector. The device status and monitored parameters are continuously stored in an internal log memory and can be transferred by an isolated serial connection to a PC. In addition, the front panel includes visual indicators for power ON, Treatment ON, alarms and low battery.

5.1.1.2 INE Insulated Transducer Arrays

Two sets of INE Insulated Transducer Arrays are connected to the Electric Field Generator. Each set includes a pair of arrays, with 9 serially interconnected single transducers in each

array. Each transducer array includes 8 thermistors. A single, sterile, 'ready to use' INE Insulated Transducer Array unit incorporates the following: one INE transducer array; conductive gel layer; mid-pads; medical tape; and overlapping liner. The transducer arrays are made from high dielectric constant insulated ceramic discs soldered to a flexible circuit board. The flexible printed circuit incorporates the components required for delivering the current for each ceramic plate and for measuring the temperature of the thermistors. At the set parameters, the electrodes do not cause significant heating due to dielectric losses of the insulation or induced fields in the target tissue. As an additional safety feature, the temperature of the transducer arrays is monitored by a temperature sensor. If temperature rises beyond 41°C, the device automatically shuts off.

5.1.1.3 Additional Components

In addition, the following components are also included in the Optune Treatment Kit: power supply, portable battery, battery rack, battery charger, connection cable and carrying case. Optune can be powered by a mains-connected power supply of 24V \pm 2 V. The power supply connects to the power connector on the front panel of the device. Alternatively, Optune can also be powered by battery using a portable, external 33 V \pm 2 V (when fully charged) rechargeable battery. Several batteries placed in a battery rack can be recharged at the same time using a dedicated battery charger, when not connected to the device. The connection between the battery and the device is through a dedicated connector on the device's front panel. The transducer arrays are connected to the device by a spiral extension cable. Patients carry the device and the battery in a specialized over-the-shoulder bag, which allows them to receive continuous treatment without changing their daily routine.

DEVICE SETTINGS AND PROGRAMMING

TTField therapy will be administered at a set frequency of 200 kHz. These treatment parameters are preset by the manufacturer such that there are no electrical output adjustments available to the participant.

DEVICE USAGE AND MAINTENANCE

The investigator, or other qualified healthcare provider from either participating site or Novocure Inc., will provide participants with training and instruction on how to operate the Optune® device for continuous at-home treatment.

Please refer to patient information and operation manual for instructions on using device.

5.1.1.4 Battery replacement

Participants will be trained to change and recharge depleted device batteries and to connect to the external power supply. Use of the external power supply does not have a time limit and can be used with either U.S. (120V AC) or European (230V AC) outlets.

For battery use: the Optune® device uses a single battery at a time. All other supplied batteries should remain in the battery charger. Each battery lasts 2 to 3 hours, and a yellow low Battery indicator light will turn on; indicating that the battery requires replacement. The treatment will continue to run while the yellow low battery indicator is illuminated until the audible alarm sounds and the red error light illuminates. Once this happens the treatment will stop and the device must be turned off and the battery replaced.

5.1.1.5 Transducer array placement and replacement

The investigator other designated healthcare provider will provide detail instructions regarding the placement/replacement and positioning of the transducer arrays on the participants head.

Placement of the transducers arrays to the head requires that the entire scalp be shaved using an electric razor (ensuring that there is no remaining stubble). The shaved scalp should be wiped with 70% isopropyl alcohol prior to placement of transducer arrays. The two black transducer arrays are to be placed in the front and back of the head and the two white arrays are placed on the sides. Removing liner covering gel on the transducer arrays, place each transducer array on head and press the entire edge of transducer array tape to the scalp.

Transducer arrays need to be replaced 1 to 2 times per week (every 4 days at most). The Optune® device's alarm will beep with increased frequency if not properly functioning, and this is a likely indicator that hair growth is preventing the transducer arrays from making good contact with the scalp. The old transducer arrays should be removed and the scalp needs to be re-shaved in order to maintain optimal contact. To ensure consistency, the new transducer arrays should be replace in the same general location as before, but a shift the transducer arrays less than an inch is permitted.

5.1.1.6 Connecting transducer arrays to device

Each of the 4 transducer array connectors with black and white connection ends must be connected to the matching sockets on the connection cable. That is, the 2 connectors with the black connection ends are to be plugged into the two black sockets and the 2 white connection ends are to be plugged into the white sockets. Press firmly to be sure the connectors are pushed in all the way.

DURATION OF EXPOSURE

Participants are required to have a minimum 18 hours per day of TTField therapy. Participant will be able to carry the device in an over-the-shoulder bag or backpack so that they can receive continuous treatment.

DEVICE STORAGE AND STABILITY

Storage conditions for the device and additional parts has an allowable temperature range of -5°C to 40°C (23°F to 104°F), and a relative humidity range of 15-75%. Storage conditions for the transducer arrays has an allowable temperature range of 5°C to 27°C (41°F to 81°F), and relative humidity range of 35-50%.

SPECIAL CONSIDERATION FOR ADMINISTRATION

5.1.1.7 Topical creams or ointments

Allow for 15 minutes after the application of a cream or ointment to the scalp before replacing transducer arrays. After 15 minutes, the scalp should be wiped again with 70% isopropyl alcohol and the transducer arrays applied to the scalp once dry.

5.1.1.8 Traveling with device

Optune's portable batteries contain lithium ion material and are restricted from being checked as luggage for passenger aircraft travel. They can be carried in the passenger cabin. The Optune device and transducer arrays will activate metal detectors.

5.1.1.9 Troubleshooting Guide

Participants should carry a copy of the Troubleshooting guide (Section 26 of the Patient information and operation manual). This guide is necessary to ensure the Optune® device is properly functioning and prevent any unwanted break in treatment. Participants that continue to experience problems with the device should contact the Principle Investigator or designated member of the study team to resolve these issues.

ACCOUNTABILITY

The Investigator, or a responsible party designated by the Investigator, must maintain a careful record of the inventory and disposition of each study device.

Responsibility for device accountability at the study site rests with the Investigator; however, the Investigator may assign some of these accountability duties to an appropriate designee. Inventory and accountability records must be maintained and readily available for inspection by the study monitor and are open to inspection at any time by any applicable regulatory authorities or other oversight bodies.

The Investigator or designee will collect and retain all used and unused components of the Optune® device treatment kit until full accounting has been completed. The Investigator or designee must maintain records that document:

- Device delivery to the study site.
- The inventory at the site.
- Device use by each participant.
- Return of device and components of treatment kit to the Investigator or designee.
- Destruction or return of device and components of treatment kit for final disposal.

These records should include dates, quantities, serial numbers (if available), and the unique code numbers (if available) assigned to the device and components of the treatment kit and study participants.

The investigational product must be used only in accordance with this protocol. The Investigator will also maintain records adequately documenting that the participants were provided with the correct investigational device specified.

Completed accountability records will be archived by the site. At the completion of the study, the Investigator or designee will oversee shipment of any remaining study drug back to Novocure, Inc. for destruction according to institutional standard operating procedures.

DEVICE RETURN

Participants are required to return used transducer arrays to the investigational site for subsequent return to manufacturer. Upon participant withdrawal from the study or upon completion of treatment, participants are required to return the Optune® device and any used or unused components of the treatment kit to the investigational site for return to manufacturer.

6. TREATMENT PLAN

6.1 DOSAGE AND ADMINISTRATION

In this study, a treatment cycle is defined as 4 weeks (or 1 month). Using the Optune® device, participants will receive multiple 1-month treatment courses, in which TTField therapy will be administered to the participants' head continuously (18-24 hours per day) for the entire duration of the 12 month study, or until disease progression, whichever comes first.

Treatment will be administered on an out-patient basis. Reported adverse events and potential risks are described in Section 9. No investigational or commercial agents or therapies other than those described in this protocol may be administered with the intent to treat the participant's malignancy.

ELECTRIC FIELD

Participants receiving TTField therapy will have 4 transducer arrays placed on their scalp and connected to the portable Optune® device which will be set to generate 200 kHz electric field in 2 perpendicular directions that are operated sequentially. The field intensity will be set at >0.7 V/cm at the center of the brain. These device settings are preset by the manufacturer. Participants will receive detailed written instructions and practical training by the Principle Investigator or designated member of the study team on how to operate the device for continuous at-home treatment.

TRANSDUCER ARRAY PLACEMENT

TTFields are applied to the shaved scalp via two pairs of orthogonally positioned transducer arrays. Since no brain metastatic lesions are present (or clinically observable) at time of enrollment, there is no need to precisely position arrays around a tumor as is the case in treating GBM.^{20,21} Instead to create the 2 perpendicular field directions, each pair of transducer arrays will be centered on the participants head such that one pair is placed on the left and right side of the head, and the second pair placed anteriorly and posteriorly. Transducer arrays should be replaced every 2 to 3 days, with a slight relocation of the new arrays ~2 cm from prior location (**Figure 4**).

[figure not shown]

Figure 4: Transducer array layouts found to deliver a uniform field distribution to the entire brain. Each layout comprises two pairs of arrays. One layout comprises the pairs of arrays shown in schematics A and B. The second layout comprises the pairs of arrays shown in schematics C and D.

6.2 TREATMENT INTERRUPTIONS AND DELAYS

Although uninterrupted treatments are preferred, participants are allowed 2 daily breaks in treatment not to exceed 1 ± 2 hours each for personal needs (e.g. bathing). Additionally, participants are allowed to suspend TTField treatment for 2 ± 1 days at the end of each 4 week treatment cycle.

TTField therapy may be delayed for up to 8 weeks (i.e., two treatment cycles) for any reason, but should be clearly documented in the case report form (CRF). If TTField therapy is not restarted after a delay of two treatment cycles, then the participant will be removed from the study.

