Participants with either LS-SCLC or ES-SCLC must be no more than 6 weeks from having received last dose of chemotherapy for primary tumor (per institutional guidelines), and must have at least demonstrated a partial response to treatment, to be considered eligible for TTField therapy with the Optune® device. Participants are encouraged to undergo TTField therapy (200 kHz) for a minimum of 18 hours per day for a period of 12 months, or until the confirmed appearance of metastatic brain lesions, whichever comes first. Participants that develop numerous (>10) supratentorial metastatic lesions before 12 months will discontinue further use of TTFields and will receive palliative/supportive care per institutional guidelines (e.g., whole brain radiotherapy). Participants that develop either limited (≤ 10) supratentorial or any number of infratentorial metastases will remain eligible to continue with TTFields therapy for the duration of the 12 months after the brain metastatic lesions are addressed according to institutional guidelines (e.g. partial brain irradiation stereotactic radiosurgery, stereotactic body radiation therapy). Systemic progression will be managed per institutional guidelines (e.g. systemic chemotherapy, immunotherapy, radiation therapy, etc.) and patients will remain eligible to continue with TTFields therapy for the duration of the 12 months. While on-study, participants will be clinically evaluated every 2-3 months per NCCN guidelines and will all be monitored remotely by phone calls monthly and will undergo gadolinium (gd)-MRI of the head at 6 months to assess occurrence of disease progression (per RECIST v1.1). Participants will be subject to periodically answering quality of life (QoL) questionnaires (i.e., baseline, 6 and 12 months after initiating treatment). At the end of study, participants will undergo clinical follow-up 1 and 3 months after completion of TTField therapy. Subsequent follow-up until death (up to 5 years) will be in accordance with standard of care (i.e., every 3 months during years 1 and 2 following last chemo-radiotherapy, then every 6 months thereafter).

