4.6 PARTICIPANT WITHDRAWAL OR DISCONTINUATION

Participants are free to withdraw consent and discontinue participation in the study at any time and without prejudice to further treatment. If a participant no longer wants to receive investigational product, but is willing to come for follow-up appointments, the participant's

request should be honored, if possible. The following are examples demonstrating why a participant's treatment might be discontinued:

- Toxicity precludes further study treatment.
- There is a need for any treatment not allowed by the protocol.
- The participant fails to meet the criteria for study treatment.
- Disease recurrence or progression.
 - TTFields therapy has been established to control supratentorial primary glioblastoma. TTFields may control supratentorial disease better than infratentorial disease. Participants that develop supratentorial metastatic lesions will be removed from the study. Participants that develop infratentorial metastases, or systemic metastases, will be able to continue with treatment for the duration of the 12 months treatment period.
- Investigator's discretion.

No further participant contact should be made if the participant withdraws consent for participation in the study. Information about the reason(s) for discontinuation and collection of any new or ongoing adverse events (AEs) should be collected at the time the participant withdraws consent.

For all other reasons for discontinuation from the study treatment phase, the participant should return to the clinic for the end of treatment (EOT) visit according to Section 7.

HANDLING PARTICIPANT WITHDRAWAL AND DISCONTINUATION

Participants that withdraw or discontinue from this study will not be replaced.

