USE IN PREGNANCY

If a participant inadvertently becomes pregnant while receiving TTField therapy, the participant will immediately be removed from the study. The site will contact the participant at least monthly and document the participant's status until the pregnancy has been completed or terminated. The investigative site will report the outcome of the pregnancy to the manufacturer without delay and within 24 hours if the outcome is a serious adverse experience (e.g., death, abortion, congenital anomaly, or other disabling or life-threatening complication to the mother or newborn). The site investigator will make every effort to obtain permission to follow the outcome of the pregnancy and report the condition of the fetus or newborn to the manufacturer.

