10.1 ANALYSIS POPULATIONS

This is a phase II multi-center single-arm pilot study to evaluate the incidence of metastatic brain lesions in participants with SCLC that receive TTField therapy. All participants that initiated TTField therapy will be considered evaluable for efficacy analysis. All participants who initiated TTFields therapy (regardless of duration) will be considered evaluable for safety. The anticipated enrollment is 106 participants, of which 45 participants will have ESCLC and 61 participants will have LSCLC.

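### Section 6.2 removes long-gap device stoppers from the study, which read literally ends the head MRIs that the 6-month primary endpoint needs

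*Combined protocol and SAP*

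**What the plan says.** Section 6.2 allows a delay in TTFields of up to 8 weeks for any reason. It then says: "If TTField therapy is not restarted after a delay of two treatment cycles, then the participant will be removed from the study". It does not say removed from treatment.

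The primary endpoint (Section 3.2) is brain metastasis from the start of TTFields to 6 months. Section 10.1 states: "All participants that initiated TTField therapy will be considered evaluable for efficacy analysis". Section 3.1 says that participants, while on study, "will undergo gadolinium (gd)-MRI of the head at 6 months to assess occurrence of disease progression". The MRI part of Section 7.1 schedules on-study Gd-MRI every 3 months for 24 months, and the 7.8 grid places the scans at weeks 12, 24 and 36. Section 7.4 describes the 3-monthly head MRI as applying in the first year during treatment.

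On stopping the device, Section 4.6 covers the case "If a participant no longer wants to receive investigational product, but is willing to come for follow-up appointments" and asks that the request be honoured where possible. The off-study list in Section 4.7 begins with "Participant requests to be withdrawn from study without further follow-up" and adds completed follow-up, death and screen failure. It has no item for a gap in device use.

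On lost outcomes, Section 4.6 says "Participants that withdraw or discontinue from this study will not be replaced". Section 10.4 allows other time points to be used, imputes nothing and permits exclusion.

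**The concern.** The endpoint and the analysis population are defined from the start of TTFields, whatever the later device use. Every participant who starts therefore needs a known brain status at 6 months. A rule that takes a participant off study for not using the device works against that, because Sections 3.1 and 7.1 tie the head MRI to being on study. A scan not taken at month 6 cannot be recovered at analysis.

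The trial has one arm, and each stage is tested against a fixed rate (40% extensive, 30% limited). Section 10.3 states no allowance for losses. Outcomes missing at random would cost power. If those who stop early also had a higher risk of brain metastasis, their absence would lower the observed incidence without any device effect, and there is no control arm in which similar losses could offset this.

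**Working it through.** **1. Who is reached on the literal reading.** A participant who last uses the device in week s is removed at week s + 8.
- Week-24 MRI: s + 8 ≤ 24 gives s ≤ 16. If 6 months is taken as 26 weeks, s ≤ 18.
- Week-12 MRI: s + 8 ≤ 12 gives s ≤ 4, so only very early stoppers also lose that scan.

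A metastasis found before removal is still an event. The exposed group is those who stop by about week 16, do not restart, are alive and have no metastasis found so far.

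**2. What happens if 6.2 means treatment only.** The participant stays on study. Section 3.1 then gives the 6-month head MRI. Section 7.1 gives 3-monthly MRIs to month 24, well past the 12-month treatment period, so it must cover people off the device. Section 7.6 and the 7.8 footnote add standard-of-care imaging counted from the last chemo-radiotherapy. That date is at most 6 weeks before the start of TTFields (Section 4.1, criterion 4), so a visit 26 weeks after it falls at about weeks 20 to 26 from Day 1, whenever the device was stopped. Only the wording of 7.4 points the other way.

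**3. The plan's own sample sizes.** Inputs from Section 10.3: two-sided exact test at 5%, 40% against 20% with n = 45, and 30% against 15% with n = 61. The lower cutoff c is the largest count with P(X ≤ c | n, p0) ≤ 0.025.
- Extensive stage: c = 11, null lower-tail probability 0.0216, power 0.826.
- Limited stage: c = 11, null lower-tail probability 0.0248, power 0.804.

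These are also the smallest n reaching 80% power under this test, so the stated figures reproduce and contain no margin for losses.

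**4. Effect of unseen outcomes.** The documents give neither the share unseen (u) nor the risk of the unseen relative to average (r), so both are assumptions. Power is for loss at random. The false-reduction column assumes no device effect, exclusion of the unseen, and r = 1.25, 1.5 and 1.75. The rate in those seen is then p0(1 − u·r)/(1 − u). For example, with p0 = 0.40, u = 0.20 and r = 1.5, it is 0.40 × 0.70/0.80 = 0.35. Where n(1 − u) is not whole, both roundings are shown.

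| Stage | u | n | c | Power | Chance of a false reduction at r = 1.25 / 1.5 / 1.75 |
|---|---|---|---|---|---|
| Extensive | 5% | 42 | 10 | 0.795 | 0.025 / 0.029 / 0.034 |
| Extensive | 5% | 43 | 10 | 0.771 | 0.019 / 0.023 / 0.027 |
| Extensive | 10% | 40 | 9 | 0.732 | 0.022 / 0.030 / 0.042 |
| Extensive | 10% | 41 | 9 | 0.704 | 0.017 / 0.024 / 0.033 |
| Extensive | 20% | 36 | 8 | 0.716 | 0.039 / 0.073 / 0.126 |
| Limited | 5% | 57 | 10 | 0.772 | 0.028 / 0.032 / 0.037 |
| Limited | 5% | 58 | 10 | 0.754 | 0.023 / 0.027 / 0.031 |
| Limited | 10% | 54 | 9 | 0.714 | 0.026 / 0.035 / 0.047 |
| Limited | 10% | 55 | 9 | 0.694 | 0.022 / 0.030 / 0.040 |
| Limited | 20% | 48 | 7 | 0.567 | 0.022 / 0.041 / 0.074 |
| Limited | 20% | 49 | 8 | 0.690 | 0.042 / 0.074 / 0.124 |

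The cutoff is a whole number, so power does not fall smoothly with n.

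**The case against.** The strongest reply is that the protocol uses this phrase loosely for stopping treatment. Section 4.6 says "Participants that develop supratentorial metastatic lesions will be removed from the study", but within a list of reasons for ending treatment, and Sections 3.1 and 6.3 describe widespread supratentorial disease as a reason to stop the device. The pregnancy rule in 6.4 says "the participant will immediately be removed from the study", yet the site then contacts her at least monthly. Section 7.6 follows all participants for survival after TTFields ends, so removal cannot mean the end of all contact. On this view the scans continue, the restriction in 7.4 merely describes a section about assessments during treatment, and Section 10.4 can use another scan where one is missing.

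Much of this stands. A reader might infer that device stoppers have no assured month-6 MRI on either reading. The documents do not support that: on the treatment-only reading, 3.1 and 7.1 cover them. A reader might also infer that the trial is biased towards a false success. That is not supported either, because no stopping rate or excess risk is given and several conditions must hold together before an outcome is lost through 6.2.

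The reply does not settle which reading applies. Section 6.3 shows that treatment-only wording was available, and 6.2 does not use it. The 4.6 provision concerns participants who ask to stop and holds only where possible. The 4.7 list is introduced as what the criteria include, so it may not be exhaustive. Four sites could act differently. Another time point helps only if a suitable scan exists, and a clear scan before month 6 does not establish status at month 6.

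**Conclusion.** The concern holds as a conflict in wording that touches the primary outcome. Followed as written, 6.2 ends the on-study head MRIs for those who stop by about week 16, while 10.1 still counts them. Read as treatment discontinuation, the gap largely closes.

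The demonstrated harm is modest and its size is unknown. Under assumed random loss of 5 to 10%, power falls from 83% to 70-80% in extensive stage and from 80% to 69-77% in limited stage. Limited stage starts so close to 80% that even a 5% loss takes it below target. Bias is small at 10% or less unseen: the chance of a false reduction stays at or below about 5%, against 2.2% and 2.5% with full data. It becomes material only if about 20% or more go unseen and carry clearly higher risk. At 1.5 to 1.75 times average risk it is then about 7 to 13%, or 4 to 7% for limited stage with n = 48. The change should be made because it is cheap. Confidence is medium, since the intended reading is open.

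**What to change.** In 6.2, replace removal from the study with wording such as: *the participant will discontinue TTFields but remain on study for follow-up, and the head MRIs in Section 7.8 (weeks 12, 24 and 36 from Day 1) will continue unless consent is withdrawn or the participant dies.* In 7.4, delete the clause that limits the 3-monthly head MRI to the time on treatment, so that it agrees with 7.1.

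The 7.8 grid, the sample sizes, the test and the rule on when device use ends all stay as they are. The cost is two wording changes and the effort of obtaining a few scans from device stoppers, which 7.1 already calls standard of care. How a scan that is still missing should be counted is a separate question.
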